## MEDICAL PROTOCOL (HRP-590)

PROTOCOL TITLE: Magnesium sulfate as adjuvant analgesia and its effect on opiate use by post-operative transplant patients in the pediatric ICU.

VERSION DATE: 06/09/2022

efficacy, the data and adverse event review will be completed after every 5 patients for duration of the study, unless any clinically relevant items deem alteration of these review intervals. Any serious or unexpected events will be thoroughly investigated followed by a short report independent of the above 3 and 5 patient review intervals. PI is responsible for notifying safety monitor via telephone or email of any events within 1 day that she or trial team are made aware.

We do not predict any adverse events to occur at our protocol dosing based on available literature. If a SAE, Unanticipated Problem Involving Risks to participants or Others (UPIRTSO) or other event causing risk to the research participants occurs, the clinical research team will notify safety monitor immediately. Safety monitor will assure the study is conducted in accordance with the investigator's agreement, the investigational plan, the IND and other applicable FDA regulations, and conditions of approval imposed by the reviewing IRB or FDA. Research will be suspended immediately if any life-threatening events occur due to magnesium.

An Annual Report will be compiled by the research team and will include a list and summary of AEs. In addition, the Annual Report will address (1) whether AE rates are consistent with pre-study assumptions; (2) reason for dropouts from the study; (3) whether all participants met entry criteria; (4) whether continuation of the study is justified on the basis that additional data are needed to accomplish the stated aims of the study; and (5) conditions whereby the study might be terminated prematurely.

The Annual Report will be sent to the safety monitor and will be forwarded to the IRB and FDA. The IRB and other applicable recipients will review progress of this study on an annual basis.

Below outlines definitions and specifics regarding relevant events:

## Safety and Adverse Events

### ***A. Definitions***

#### ***Adverse Event***

An ***adverse event*** (AE) is any symptom, sign, illness or experience that develops or worsens in severity during the course of the study. Intercurrent illnesses or injuries will be regarded as adverse events, whether or not considered intervention-related. Abnormal results of diagnostic procedures are considered to be adverse events if the abnormality:

- results in study withdrawal
- is associated with a serious adverse event
- is associated with clinical signs or symptoms

## MEDICAL PROTOCOL (HRP-590)

PROTOCOL TITLE: Magnesium sulfate as adjuvant analgesia and its effect on opiate use by post-operative transplant patients in the pediatric ICU.

VERSION DATE: 06/09/2022

- leads to additional treatment or to further diagnostic tests
- is considered by the investigator to be of clinical significance

### ***Classification of an Adverse Event***

Mild: Events require minimal or no treatment and do not interfere with the participant's daily activities  
— Moderate: Events result in a low level of inconvenience or concern with the therapeutic measures. Moderate events may cause some interference with functioning. — — Severe: Events interrupt a participant's usual daily activity and may require systemic drug therapy or other treatment. Severe events are usually potentially life-threatening or incapacitating. Of note, the term "severe" does not necessarily equate to "serious".

Of note, we do not intend to report mild side effects which are known to frequently occur in TPIAT and Liver transplants. For example, we will not report individual episodes of nausea/emasis, post-operative pain, ventilator adjustments (unless an escalation to new mode of respiratory support), non-sustained hypertension/hypotension on routine vital checks, anticipated returns to OR (for example to close abdomen after initial surgery). Similarly, known/predicted intraoperative fluctuations in coagulopathy, bleeding, and vitals trends will not routinely be reported, unless not responding to expected interventions per OR team. All of the above will be reported if medical team experts (i.e. surgeon or anesthesiologist in OR, intensivist in PICU) believe these above symptoms are contributing to an atypical course or a worsening in patient's expected trajectory.

### ***Relationship to Study Intervention***

All adverse events (AEs) must have their relationship to study intervention assessed by the clinician who examines and evaluates the participant based on temporal relationship and her/his clinical judgment. The degree of certainty about causality will be graded using the categories below. In a clinical trial, the study product must always be suspect.

Probably related: There is evidence to suggest a causal relationship, and the influence of other factors is unlikely. The clinical event, including an abnormal laboratory test result, occurs within a reasonable time after administration of the study intervention, is unlikely to be attributed to concurrent disease or other drugs or chemicals, and follows a clinically reasonable response on withdrawal (dechallenge). Rechallenge information is not required to fulfill this definition. — — Possibly Related: There is some evidence to suggest a causal relationship (e.g., the event occurred within a reasonable time after administration of the trial medication). However, other factors may have contributed to the event (e.g., the participant's clinical condition, other concomitant events). Although an AE may rate only as "possibly related" soon after discovery, it can be flagged as requiring more information and later be upgraded to "probably related" or "definitely related", as appropriate. — — Not Related: The AE is completely independent of study intervention administration, and/or evidence exists that the event is definitely related to another etiology. There must be an alternative, definitive etiology documented by the clinician.

### ***Serious Adverse Event***

## MEDICAL PROTOCOL (HRP-590)

PROTOCOL TITLE: Magnesium sulfate as adjuvant analgesia and its effect on opiate use by post-operative transplant patients in the pediatric ICU.

VERSION DATE: 06/09/2022

Adverse events are classified as serious or non-serious. A ***serious adverse event*** is any AE that is:

- fatal
- life-threatening
- requires or prolongs a hospital stay
- results in persistent or significant disability or incapacity
- a congenital anomaly or birth defect
- an important medical event based on appropriate medical judgment or that requires medical or surgical intervention to prevent one of the above outcomes listed in this definition

Important medical events are those that may not be immediately life threatening, but are clearly of major clinical significance. They may jeopardize the subject, and may require intervention to prevent one of the other serious outcomes noted above. For example, drug overdose or abuse, a seizure that did not result in in-patient hospitalization, or intensive treatment of bronchospasm in an emergency department would typically be considered serious.

All adverse events that do not meet any of the criteria for serious should be regarded as ***non-serious adverse events***.

### ***Adverse Event Reporting Period***

The study period during which adverse events must be reported is normally defined as the period from the initiation of any study procedures to the end of the study treatment follow-up. For this study, the study treatment follow-up is defined as 7 days following the last administration of study treatment or until discharge from the ICU (whichever occurs first).

### ***Preexisting Condition***

A preexisting condition is one that is present at the start of the study. A preexisting condition will be recorded as an adverse event if the frequency, intensity, or the character of the condition worsens during the study period.

### ***General Physical Examination Findings***

At screening, any clinically significant abnormality will be recorded as a preexisting condition. At the end of the study, any new clinically significant findings/abnormalities that meet the definition of an adverse event will also be recorded and documented as an adverse event.

### ***Post-study Adverse Event***

All unresolved adverse events will be followed by the investigator until the events are resolved, the subject is lost to follow-up, or the adverse event is otherwise explained. At the last scheduled visit, the investigator will instruct each subject to report any subsequent event(s) that the subject, or the subject's personal physician, believes might reasonably be related to participation in this study.

### ***Hospitalization, Prolonged Hospitalization or Surgery***

Any adverse event that results in hospitalization or prolonged hospitalization will be documented and reported as a serious adverse event unless specifically instructed otherwise in this protocol. Any condition responsible for surgery should be documented as an adverse event if the condition meets the criteria for an adverse event.

## MEDICAL PROTOCOL (HRP-590)

PROTOCOL TITLE: Magnesium sulfate as adjuvant analgesia and its effect on opiate use by post-operative transplant patients in the pediatric ICU.

VERSION DATE: 06/09/2022

Neither the condition, hospitalization, prolonged hospitalization, nor surgery are reported as an adverse event in the following circumstances:

- Hospitalization or prolonged hospitalization for diagnostic or elective surgical procedures for a preexisting condition. Surgery should **not** be reported as an outcome of an adverse event if the purpose of the surgery was elective or diagnostic and the outcome was uneventful.
- Hospitalization or prolonged hospitalization required to allow efficacy measurement for the study.
- Hospitalization or prolonged hospitalization for therapy of the target disease of the study, unless it is a worsening or increase in frequency of hospital admissions as judged by the clinical investigator.

### ***B. Recording of Adverse Events***

At each contact with the subject, the investigator must seek information on adverse events by specific questioning and, as appropriate, by examination. Information on all adverse events will be recorded immediately in the source document (i.e. within 24 hours of event notification), and also in the appropriate adverse event module of the case report form (CRF). All clearly related signs, symptoms, and abnormal diagnostic procedures results will be recorded in the source document, though should be grouped under one diagnosis.

All adverse events occurring during the study period must be recorded. The clinical course of each event will be followed until resolution, stabilization, or until it has been determined that the study treatment or participation is not the cause. Serious adverse events that are still ongoing at the end of the study period must be followed up to determine the final outcome. Any serious adverse event that occurs after the study period and is considered to be possibly related to the study treatment or study participation should be recorded and reported immediately.

### ***C. Reporting of Serious Adverse Events***

#### **1. IRB Notification by Investigator**

Reports of all serious adverse events (including follow-up information) must be submitted to the IRB within 5 working days if it falls under the UPIRTSO guidelines. Copies of each report and documentation of IRB notification and receipt will be kept in the Clinical Investigator's binder.

#### **2. FDA Notification by Sponsor**

The study sponsor shall notify the FDA by telephone or by facsimile transmission of any unexpected fatal or life-threatening experience associated with the use of the drug as soon as possible but no later than 7 calendar days from the sponsor's original receipt of the information.

If a previous adverse event that was not initially deemed reportable is later found to fit the criteria for reporting, the study sponsor will submit the adverse event in a written report to the FDA as soon as possible, but no later than 15 calendar days from the time the determination is made.

## MEDICAL PROTOCOL (HRP-590)

PROTOCOL TITLE: Magnesium sulfate as adjuvant analgesia and its effect on opiate use by post-operative transplant patients in the pediatric ICU.

VERSION DATE: 06/09/2022

Agency	Criteria for Reporting	Timeframe	Form to Use	Submission address/fax numbers
U of MN IRB	SAE : fatal, life-threatening or serious, unexpected, at least possibly related	5 working days	MedWatch 3500A Form	RNI in ETHOS
FDA	SAE : fatal, life-threatening, unexpected, at least possibly related	7 calendar days	MedWatch 3500a Form but alternative formats are acceptable (e.g. summary letter)	Fax: [name]
	SAE : serious, unexpected, at least possibly related	15 calendar days		

## 19. Provisions to Protect the Privacy Interests of Participants

**19.1. Protecting Privacy:** Patients will be given opportunity in initial consent process as to whether there are any members of medical or research team they wish to interact or not interact with, desires which will be maintained. The only members which should have direct contact, however, will include the PI and co-investigators (if on medical staff). Autonomy will be emphasized to all members of research team, including transplant surgeon (co-investigator) or PACCT physician performing initial consent, with respect for any patient who wishes not to enroll in our intervention. This will be emphasized to medical team involved in PICU care of patients as well. We do not otherwise anticipate any privacy concerns as our intervention is not dependent on any other underlying attributes other than the transplantation procedure itself. HIPAA compliance measures are otherwise routine at the institution where study is taking place. Comorbidities and transplant indication will not be identified in either control or experimental group, which should further limit potential of identifying information in final written product.

**19.2. Access to Participants:** The research team will need access to medical chart in order to collect data regarding the primary and secondary outcomes, as this is the

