### 5. Procedures Involved

#### 5.1. Study Design:

Experimental Group: Prospective Cohort of next 30 incoming liver and TPIAT transplant children which meet inclusion criteria. Due to the more difficult predictability of when liver transplants occur, and to ensure adequate enrollment of 30 patients occurs within the 3-year pilot duration, we have chosen not to have a 50/50 balanced prospective cohort.

Control Group: Control will be via retrospective chart review of the last 60 transplant patients from the same population (liver, TPIAT) with same surgeon. Intervention and data collection will be as outlined elsewhere in protocol.

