## 10. Local Number of Participants

- 10.1. Local Number of Participants to be Consented: Local Number of Participants to be Consented: 30 consented for prospective cohort, 60 previous patients for control group. Assuming ~75% consent rate, this will require ~40 patients approached.

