### Standard Reporting

2. type of transplant received
3. age
4. weight
5. height
6. gender

*15.2. Power Analysis:* Power analysis was performed based on pediatric studies by Hutchins et al and Jabbour et al (see references section 24), indicating 90 patients in order to see a detectable difference of 20% between study groups with 80% power. This would detect a decrease of nearly 3.5 mg/kg over a 7 day PICU course, and seemed a reasonable target for our hypothesis. Given the progression of IND review, this number will be reduced to 60 for the retrospective cohort (renal transplants removed from study), and 30 for prospective cohort (typical target for pilot-based study), to simulate a pilot study rather than fully correlational study. Regardless, original power analysis is shown below:

n per group	Detectable difference between groups (Total 1st 7 days in morphine equivalent mg/kg)		Detectable difference between groups (% reduction in dose)	
	80% power	90% power	80% power	90% power
40	5.26	6.09	29	33
50	4.70	5.43	26	30
60	4.28	4.95	24	28
70	3.96	4.58	23	26
80	3.70	4.28	21	24
90	3.49	4.03	20	23
100	3.30	3.82	19	22
110	3.15	3.64	18	21
120	3.01	3.49	18	20

Based on a pooled SD estimate for total morphine equivalent dose first 7 days post-op of 8.3 mg/kg (Hutchins 2016), the table lists the minimum differences (in mg/kg) that are detectable with 80% and 90% power for various enrollment sizes. These differences are also presented in terms of the % reduction in total dose, based on an overall mean total dose of 15.5 mg/kg (Hutchins 2016). For comparison, a 29.5% reduction in total dose (first 48h) in ketamine + magnesium versus ketamine was observed in Jabbour 2014.

*15.3. Statistical Analysis:* The primary analysis will compare the total morphine equivalent dose per kg during the PICU stay between experimental and historical control groups. Total dose will be compared in both unadjusted analyses and adjusted analyses using linear models, with a covariate for study group and adjusting covariates for transplant type, age, and gender, to account for potential variation due to these factors. Distributional assumptions will be examined and data transformations will be used as appropriate. Secondary outcomes will be compared using similar approaches using generalized linear models for count

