## MEDICAL PROTOCOL (HRP-590)

PROTOCOL TITLE: Magnesium sulfate as adjuvant analgesia and its effect on opiate use by post-operative transplant patients in the pediatric ICU.

VERSION DATE: 06/09/2022

only place data is stored/located. We will only search chart in specific areas that our outcome measures are located, and will avoid all other unnecessary information. Some of the data elements need more diligent, subjective searches than what can be consistently and reliably obtained by computer data extraction techniques (which were discussed during development process). Specifically, the EMR will be accessed for appropriate patient by MRN, followed by selecting the appropriate surgical encounter, followed by only specific portals in epic where intended data elements are located (i.e. Intake/Output or results review -> magnesium level, etc). The PI and co-investigators, however, will have more frequent and expanded access to chart in circumstances where they are the medical provider taking care of patient for the day (unrelated to research itself), since that person may be directly involved in patient care. All of the patients are otherwise within the co-investigator's (transplant surgeon) and PI's (PICU physician) practice area.

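### Pre-operative opioid use is neither collected nor adjusted for in a historical-control comparison of opioid dose, so within-transplant-type imbalance could bias the primary result in either direction

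*Combined protocol and SAP*

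**What the plan says.** The comparison is not randomised. Section 5.1 states: "Control will be via retrospective chart review of the last 60 transplant patients from the same population (liver, TPIAT) with same surgeon". Section 10.1 gives the sizes: "30 consented for prospective cohort, 60 previous patients for control group". The controls are 30 liver and 30 TPIAT patients. For the treated group Section 5.1 says that "we have chosen not to have a 50/50 balanced prospective cohort".

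Section 15.3 will "compare the total morphine equivalent dose per kg during the PICU stay between experimental and historical control groups", both unadjusted and in a linear model with "adjusting covariates for transplant type, age, and gender, to account for potential variation due to these factors". A two-sided 5% test is specified. The section describes no matching, calendar-time term or sensitivity analysis for unmeasured confounding.

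Section 15.1 lists what will be taken from the medical record for analysis. Its baseline items are transplant type, age, weight, height and gender. Nothing concerns opioid use, pain or analgesic treatment before surgery. Section 15.1 says that a separate attachment repeats these measures.

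Two passages bear on whether such an item could be picked up anyway. Section 19.2 says: "We will only search chart in specific areas that our outcome measures are located, and will avoid all other unnecessary information". Section 19.1 says: "Comorbidities and transplant indication will not be identified in either control or experimental group".

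**The concern.** The outcome is opioid dose. A child who already takes opioids regularly may need more after surgery whether or not magnesium is given, so prior use is an obvious candidate confounder. It is fixed before treatment, so adjusting for it would not remove part of a magnesium effect.

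The plan gives reasons to expect that the groups might differ on it:

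- **Era.** Section 25.1 predicts about 10 to 20 patients a year. If past volume was similar, 60 controls span 60/20 = 3 to 60/10 = 6 years, all before an enrolment period of about 3 years (Section 5.3). Section 2.3 itself refers to an opioid crisis and shortage, so prescribing may have changed over that time.
- **Selection.** Treated patients must consent (about 75% expected, Section 10.1), have study staff in the hospital on the day, and pass an investigator-judgement exclusion (Section 8.2). Controls come from a list, with only the opt-out, age and creatinine exclusions.

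The transplant-type covariate deals with liver-versus-TPIAT differences in the adjusted model. It does not deal with differences within liver or within TPIAT. If the share of previously exposed children differs there, the difference is attributed to magnesium, and the planned data could not show that this had happened.

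**Working it through.** **Inputs from the protocol.** SD 8.3 mg/kg and overall mean 15.5 mg/kg for the 7-day total (Section 15.2); two-sided 5% test (Section 15.3); 60 controls and 30 treated (Section 10.1). The SD is for the first 7 days, while Section 15.3 analyses the PICU stay. It is used here as the only SD given.

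**Inputs assumed.** The documents give neither the prevalence of pre-operative opioid use nor its effect on post-operative dose. Assumed: exposed children need 5 to 10 mg/kg more, and the prevalence within transplant type differs by 10 to 20 percentage points between the groups.

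**Step 1: the plan's own figure.** With 90 per group, SD 8.3 and 80% power, the two-sample t-test (noncentral t) gives a detectable difference of 3.485 mg/kg, against 3.49 in the Section 15.2 table. The normal-approximation sample size for 3.49 mg/kg is 89 per group against 90. The percentage column treats 15.5 as the mean over both groups: 3.49 / (15.5 + 3.49/2) = 3.49/17.245 = 20.2%, printed as 20%. The table is reproduced, and 3.49 mg/kg is taken as the yardstick.

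**Step 2: precision of the planned comparison.** SE = 8.3 × √(1/60 + 1/30) = 8.3 × √0.05 = 1.86 mg/kg. The smallest observed difference that reaches significance is about 1.96 × 1.856 = 3.64 mg/kg. At 60 versus 30, power for 3.49 mg/kg is about 46%, and the difference detectable with 80% power is 5.26 mg/kg. This SE makes no allowance for variance that the three planned covariates may explain.

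**Step 3: bias.** Bias b = (difference in prevalence) × (extra need per exposed child). With no true effect, the false-positive rate by normal approximation is 1 − Φ(1.96 − b/SE) + Φ(−1.96 − b/SE).

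| Imbalance | Extra need (mg/kg) | Bias (mg/kg) | Share of 3.49 | Bias/SE | False-positive rate |
|---|---|---|---|---|---|
| 10 points | 5 | 0.5 | 14% | 0.27 | 5.8% |
| 10 points | 10 | 1.0 | 29% | 0.54 | 8.4% |
| 20 points | 5 | 1.0 | 29% | 0.54 | 8.4% |
| 20 points | 10 | 2.0 | 57% | 1.08 | 19.0% |

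**Step 4: wider assumptions.** An imbalance of 10 points with 3.1 mg/kg extra need gives 0.31 mg/kg and a rate of 5.3%. An imbalance of 30 points with 10 mg/kg gives 3.0 mg/kg and 37%. The answer therefore runs from negligible to serious, depending on two quantities that the plan does not collect.

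**The case against.** The strongest counter-argument is that the size is wholly assumed. No document gives a prevalence, an effect or a drift over time. An extra need of 5 to 10 mg/kg is 5/15.5 = 32% to 10/15.5 = 65% of the overall mean, and at the low end the effect on the error rate is trivial. This stands. The figures illustrate what is possible and do not estimate what will happen.

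There are also partial safeguards: same surgeon, same institution, same age range, same creatinine exclusion, and adjustment for transplant type. These narrow the concern to imbalance within transplant type, but none of them measures prior opioid use. Section 15.2 presents the study as simulating a pilot, and Section 10.1 allows a smaller target to show feasibility. That lowers the stakes, but Section 15.3 still specifies a 5% test of this comparison.

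Three stronger readings are tempting and are not supported:

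- A reader might infer that Section 19.1 forbids recording the variable. Its stated aim is to limit identifying information in the final written product, so it may mean only that the items are not reported. Opioid use at admission is also neither a comorbidity nor an indication. The omission is shown by the Section 15.1 list, and the practical barrier is the chart-search limit in Section 19.2.
- A reader might infer that the bias favours magnesium. Nothing indicates a direction, and a real effect could equally be hidden.
- A reader might take 20% of 15.5, that is 3.1 mg/kg, as the target. The protocol's figure for the 20% row is 3.49 mg/kg. It belongs to the plan with 90 per group, so it serves here only as a yardstick.

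**Conclusion.** The point holds as a design gap that is cheap to close, not as a demonstrated bias. The documents establish that the comparison is non-randomised, that the adjusted model has three covariates, that the Section 15.1 list has no pre-operative opioid item, and that chart review is limited to areas holding outcome measures. It follows that imbalance in prior opioid use within transplant type would be neither seen nor corrected.

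On the assumed inputs the bias is 0.5 to 2.0 mg/kg in either direction, which is about 0.3 to 1.1 standard errors. The false-positive rate is about 6% to 19% if there is no true effect. This rests on the assumed need and imbalance, on the SD of 8.3 mg/kg carrying over to the PICU-stay total, and on the attachment matching Section 15.1 as that section says. The attachment was not available. The Standard Reporting list in the text as read starts at item 2, so the sponsor should confirm that no baseline item is missing from view.

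**What to change.** 1. Add regular opioid use at admission to the Section 15.1 data list: yes/no, and daily morphine equivalents per kg where recorded. Use the same equianalgesic conversions as for the outcome.
2. Abstract it by the same rule in both groups, including patients already enrolled, and report its completeness by group.
3. Include it as a covariate in the adjusted primary model in Section 15.3. Keep post-operative co-analgesics out of that model, because magnesium may affect them.
4. Amend the chart-search limit in Section 19.2 to allow the field. If needed, clarify whether Section 19.1 means not recorded or not reported.

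The record is already opened for all 90 patients, some items already need manual searching (Section 16.6), and every TPIAT patient has a routine pre-operative pain-specialist visit (Section 11.1). No new procedure or patient contact is needed.

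The cost is one more field in 90 charts, including any control charts already abstracted, dose conversion where amounts are listed, a small IRB amendment and one model parameter. Historical records may be incomplete. If the variable predicts dose it would also narrow the interval, but the documents do not allow that gain to be quantified. Other differences between eras would remain, so the result should still be reported as a historical-control comparison.
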